6.2 Missing Data

No assumption or statistical method will be used in case of missing data. No censoring of data will be performed.

6.3 Analysis methods

6.3.1 Observational study (Observational cohort)

6.3.1.1 Primary analysis of primary endpoint

In the observation cohort a comparison between the high- and low-risk stratum will be conducted using an unadjusted Cox-regression model with log-rank test.

In addition, adjustment for age, gender, Hba1c, systolic blood pressure, retinopathy eGFR and UACR at baseline will be conducted.

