## 15.7 Analysis of secondary endpoints

All secondary endpoints as described in section 5.5 will be analyzed to test if there is a difference in development of endpoints over time between a) active vs. placebo treated patients, and b) high-risk and low-risk population based on CKD273. As described in section 15.5.1 the analyses will initially compare low-risk with high-risk placebo treated patients, and secondly all high-risk patients. Adjustments will be performed as for the primary endpoint.

In addition to time to event (survival) analyses for discrete endpoints, analyses will evaluate the change over time in geometric mean UACR as slope analyses unadjusted as well as adjusted for confounders as described for the primary endpoint, comparing slope in the high-risk population with active vs. placebo and between low-risk and high-risk population the total population. Similar analyses will be performed with change in eGFR with time as the endpoint.

In the analyses with time to cardiovascular events, only time to first event in case of more than one event in a patient will be included.

In addition to the above described analyses comparing endpoints or slopes in high- vs. low-risk population or active vs. placebo, explorative analyses will also evaluate if the CKD 273 pattern and other baseline variables or changes in variables from baseline to 13 weeks visit in the high-risk population are predictive of development of endpoints.

Further analyses may be described in the SAP before database lock.

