4 STATISTICAL PRINCIPALS

4.1 Confidence limits and significance level

Any p-value below 0.05 will be considered statistically significant. A p-value will be calculated for the primary analysis. P-values for the secondary analyses will only be calculated if the primary analysis yields a p-value below 0.05. For all primary and secondary analyses 95 % confidence limits will be calculated.

Continuous values fulfilling terms of normal distribution will be displayed as mean values and 95 % confidence limits of the mean. Variables not fulfilling terms of normal distribution will be displayed as median and inter quartile range from p25 to p75.

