6.3.1.3 Sensitivity analysis

In order to out-balance the fact that the "high"-risk stratum has primary outcome measures every third month we will perform a sensitivity analysis on the primary endpoint. Any primary endpoint in the "high"-risk stratum between annual visits will be carried forward to the date of the following annual visit. This analysis is most likely underpowered because of exclusion of endpoints in the high-risk stratum, however, the trend of the primary analysis is expected.

As in the "high"-risk group we have participants allocated to either active IMP or placebo we potentially limit the number of endpoints if the active IMP is beneficial. To adjust for this potential effect, we will perform a sensitivity analysis on the primary endpoint only in "low"-risk participants and in "high"-risk participants allocated to placebo treatment. This analysis is most likely also underpowered because of exclusion of endpoints in the "high"-risk stratum, however the trend of the primary analysis is expected.

ANOVA models for each continuous variable measured at baseline: age, HbA_{1c}, systolic blood pressure, Study site, eGFR and UACR will be tested within each stratum "high"- and "low"-risk as well as interaction in the Cox-model between strata with the primary endpoint as determinant. Chi square tests will be used for categorical variables: gender, use of antihypertensive agents, known cardiovascular disease and retinopathy.

We expect a correlation between the “high”-risk stratum and events of the primary endpoint for participants with known risk factors for overt kidney disease (higher age, HbA_{1c}, systolic blood pressure, UACR, and lower eGFR, male gender, use of antihypertensive agents, known cardiovascular disease and retinopathy).

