6.4 Additional analysis

For the per protocol cohort Cox-regression models will be performed both unadjusted and adjusted using treatment allocation as determinant and testing the primary outcome. Adjustment will include: Age, gender, HbA_{1c}, systolic blood pressure, retinopathy, eGFR and UACR at baseline. To examine added value for discrimination rIDI will be calculated for on all above described Cox-regression models.

In the observational cohort excluding all participants allocated to active treatment Cox-regression models will be performed to evaluate the hazard ratio between the “high”-risk without potential influence of the active treatment and the “low”-risk stratum. The model will be performed both on all available data and on censored data only (including annual samples). The models will be achieved unadjusted and adjusted for Age, gender, HbA_{1c}, systolic blood pressure and presence of retinopathy, eGFR and UACR at baseline. To examine added value for discrimination the rIDI will be calculated for all above described Cox-regression models.

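### SAP 6.3.1.1 compares the risk strata on unequal UACR schedules, so without a drug effect the hazard ratio can exceed 1 even if CKD273 predicts nothing

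*SAP*

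**What the plan says.** - **Analysis (SAP 6.3.1.1).** "In the observation cohort a comparison between the high- and low-risk stratum will be conducted using an unadjusted Cox-regression model with log-rank test". No visits are excluded. The cohort (SAP 4.3.2) includes the actively treated patients.
- **Schedule (Protocol 6.2, 6.3, Table 1).** UACR is measured every 13 weeks in the high-risk group and annually in the low-risk group. Both also have an end-of-study assessment.
- **Endpoint (SAP 6.1.1, Protocol 5.4 and 10.9).** It is judged on three consecutive morning voids around one visit. No later visit has to confirm it.
- **Sensitivity analyses (SAP 6.3.1.3).** The SAP names the unequal schedule. A high-risk endpoint between annual visits "will be carried forward to the date of the following annual visit", and the text adds "This analysis is most likely underpowered because of exclusion of endpoints in the high-risk stratum". A second analysis drops the active arm because "we potentially limit the number of endpoints if the active IMP is beneficial", but it leaves the looks unequal.
- **Additional analysis (SAP 6.4).** For low-risk against high-risk placebo: "The model will be performed both on all available data and on censored data only (including annual samples". SAP 6.2 states "No censoring of data will be performed".
- **Hierarchy (SAP 4.1).** "P-values for the secondary analyses will only be calculated if the primary analysis yields a p-value below 0.05".

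**The concern.** UACR varies from visit to visit, and one qualifying visit is enough. The stratum that is looked at more often therefore has more chances to qualify. CKD273 status itself sets the schedule, so the distortion runs in the direction of Hypothesis 1.

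This is the trial's primary objective. The same endpoint feeds sensitivity, specificity and ROC in SAP 6.3.1.2, where a significant unadjusted CKD273 hazard ratio also triggers the rIDI. If the primary analysis in SAP 4.1 means 6.3.1.1, it also decides whether secondary p-values are calculated.

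The planned safeguard could mislead. SAP 6.3.1.3 expects the carry-forward to show the same trend as the primary analysis, and agreement would reassure little if both carry the same bias.

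**Working it through.** **1. The plan's own figures.** The documents give no look ratio and no power for high against low risk. The 129 per arm in SAP 3.4 concerns the randomised comparison and has no bearing here. The planning incidences do: 8.5% low-risk, 40% high-risk placebo, 24% high-risk active. Pooled high-risk incidence is (40% + 24%)/2 = 32%. The implied hazard ratios are ln(0.68)/ln(0.915) = 4.34 pooled and ln(0.60)/ln(0.915) = 5.75 for placebo.

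**2. Looks from Table 1.** At 230 weeks: 17 periodic + 1 = 18 against 4 + 1 = 5, ratio 3.6. At 104 weeks, with end of study merged into the week 104 visit: 8 against 2, ratio 4.0. Over 104 to 230 weeks the ratio runs from 3.0 to 4.0, mean 3.56.

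**3. Extreme case.** Treat every look as an independent chance. An incidence of 8.5% over 5 looks gives 1 − 0.915^(1/5) = 1.76% per look. Over 18 looks that becomes 1 − (1 − 0.0176)^18 = 27.4%. The ratio of cumulative hazards equals the ratio of looks, 3.6.

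**4. Simulation with no CKD273 effect and no drug effect.** From the documents: 1811 patients, 15% high-risk (272 against 1539), the SAP endpoint rule, follow-up of 104 to 230 weeks (taken as uniform), and low-risk incidence calibrated to about 8.5%. Assumed: between-patient SD of log UACR 0.7, and the noise and drift shown. Carried-forward endpoints are dated to the next annual visit or end of study.

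| Visit SD / void SD / mean yearly drift (log scale) | Incidence low / high | HR all looks | HR carried forward | HR common visits | Rejection at 0.05: all / carried / common |
|---|---|---|---|---|---|
| 0 / 0.05 / 0.10 | 8.9% / 9.1% | 1.05 | 1.03 | 1.03 | 7% / 6% / 5% |
| 0 / 0.35 / 0.06 | 8.7% / 12.6% | 1.51 | 1.49 | 1.05 | 55% / 51% / 5% |
| 0.3 / 0.4 / 0.05 | 8.7% / 16.3% | 2.03 | 1.99 | 1.04 | 95% / 93% / 4% |
| 0.5 / 0.4 / 0 | 8.7% / 18.3% | 2.30 | 2.25 | 0.97 | 100% / 100% / 3% |
| 0.7 / 0.5 / 0 | 9.1% / 20.4% | 2.50 | 2.44 | 0.95 | 100% / 100% / 3% |

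Hazard ratios come from 60,000 simulated patients, rejection rates from 150 to 300 trials. Adjusting the all-look model for baseline UACR does not remove the bias (1.09 to 2.73).

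**5. A wider grid, 200,000 patients per stratum, same null.**

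| Setting | All visits | Carried forward |
|---|---|---|
| Slow drift | 1.41–2.04 | 1.38–1.99 |
| Faster drift | 1.15–1.46 | 1.13–1.43 |
| Strong true progression | 1.06–1.23 | 1.04–1.20 |

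Without noise the all-visit value is 1.02, and with irreversible onset 1.01. On common visits it is 0.99–1.01, with 4–6% rejection. The fate of endpoints with no following annual visit (8.5–21% of high-risk endpoints) matters: if they are dropped, the three carried-forward ranges become 1.23–1.82, 0.94–1.21 and 0.82–0.95. Of low-risk endpoints, 26–38% are first detected at end of study.

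**6. Consequences.** A true common-visit hazard ratio of 1.5 or 2.0 reads as 1.62–2.96 or 2.18–3.95 on all visits. For a useless test, sensitivity reads 15.5–25% instead of 15%. Outcome D (one void) gives 1.08–1.97 on all visits and 0.99–1.01 on common visits.

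**7. With a drug effect.** Suppose spironolactone lowers UACR by 20–30% in the active half (the range in Protocol 4.1 for proteinuric patients) and CKD273 still predicts nothing. The pooled hazard ratio is then 0.83–1.60 on all visits and 0.61–0.88 on common visits. Placebo against low-risk on common visits stays at 0.99–1.01.

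**The case against.** **The SAP already discloses this.** True in part. SAP 6.3.1.3 names the schedule and the drug effect, and SAP 6.4 plans an equal-look model. But the rule meant to balance the schedule changes dates and keeps the endpoints, and the model that works is only additional. The remark about excluded endpoints is ambiguous. It may refer to endpoints with no following annual visit, or to an intention to drop interim endpoints that the rule does not carry out.

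**The size is assumed.** This stands. With little reversible variation the bias is close to nil. Moving patients who stop study drug to annual visits (Protocol 14.6) also narrows it: with 30% stopping, 2.03 becomes 1.89 and 1.42 becomes 1.36.

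**The remedy has its own bias.** Partly right. Reached endpoints are flagged, and participants not on ACE/ARB at screening are to start only after that (Protocol 12.4). Assume half start 4–26 weeks after an interim endpoint, with a 30% fall in UACR. The null hazard ratio on common visits is then 0.81–0.95 for placebo against low-risk. That is conservative for Hypothesis 1, whereas the all-visit bias favours it.

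**A reader might infer that the protocol requires placebo-only as the tested comparison,** because Protocol 15.7 says "the analyses will initially compare low-risk with high-risk placebo treated patients, and secondly all high-risk patients". The documents do not support that. Section 15.7 covers secondary endpoints and refers back to a section 15.5.1 that does not exist. Protocol 15.6 and 15.2 and SAP Hypothesis 1 compare the whole risk populations. Equal looks and the choice of high-risk population are separate decisions, and the schedule argument supports only the first.

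**Conclusion.** The point holds and should be fixed. Without a drug effect, the 6.3.1.1 hazard ratio can exceed 1 although CKD273 predicts nothing, and the carry-forward leaves that almost unchanged. The direction follows from the schedule and the single-visit endpoint. The size rests on assumed UACR variability: a null hazard ratio from about 1.0 to about 2.0–2.5. With a working drug, the pooled estimate mixes an upward schedule bias with a downward drug effect and can fall below 1.

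A reader might infer that any positive result would be an artefact of the schedule. The documents do not support that: even the extreme case in step 3 gives 3.6, below the pooled planning value of 4.34. The risk lies with modest hazard ratios. Nor is every outcome open to the same correction. Hyperkalaemia (K) counts at any time point, and the version of I measured from month three has no low-risk counterpart.

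**What to change.** 1. **SAP 6.3.1.1:** detect and date the primary endpoint only at assessments scheduled in both strata, that is annual visits plus end of study. Keep the all-visit analysis as a sensitivity analysis.
2. **Other high-against-low comparisons:** use the same visits for the 2x2 and ROC measures and for outcomes D, E, F, G and the from-baseline version of I. Of these outcomes only D was sized; the others share the unequal schedule. Do not apply the rule to K or to the month-three version of I; note their unequal ascertainment instead.
3. **Population:** report the common-visit comparison both pooled and for low-risk against high-risk placebo, because a drug effect lowers the pooled value. Which one is tested is the sponsor's choice and must be reconciled with Protocol 15.6.
4. **SAP 6.3.1.3:** re-evaluate the endpoint at the common visits in place of the carry-forward, or state that it corrects dates only. Say what happens to an endpoint with no following annual visit.
5. **SAP 6.4:** define the censored, annual-sample data set, say whether end of study counts, and reconcile it with SAP 6.2.

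**Cost.** No new data are needed. Restricting visits is a SAP wording change; testing placebo-only would also depart from Protocol 15.6. In the model, 5–45% of high-risk endpoints leave the comparison. Power on common visits is 54–61% pooled and 33–40% placebo-only at a true hazard ratio of 1.5, and 94–97% and 79–85% at 2.0. At the planning figures placebo-only power is about 100%, and 99.3% if a third of placebo endpoints are lost. With the ACE/ARB starts assumed above, placebo-only power at 2.0 falls to 42–79%, which is one reason to keep the all-visit analysis alongside.

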	
The expected relative proportions of diabetes type 2 patients developing microalbuminuria in our study population are: 24% in patients at high-risk for diabetic nephropathy in the treatment group, 40% in those patients at high-risk for diabetic nephropathy in the placebo group and 8.5% in those therapy-naive patients at low-risk for diabetic nephropathy. Using the samples size formula for two proportions test (<math>\alpha=0.05</math> <math>\beta=0.80</math>), randomized (1:1), <math>n=129</math> in each arm of the intervention group. To account for drop-outs we plan to randomize 300 in all. It is expected that approx. 15% of the population will show a pattern of high-risk of CKD, therefore 2000 patients have to be included. Equal drop-out frequency is expected in both groups and there will be no replacement of drop-out. Discontinuation prior randomization is categorized screening failure.
 
Analysis populations: The primary analysis will be conducted for all patients included (intent-to-treat population) in the observational and intervention study groups. In addition, all relevant efficacy endpoints will be also analyzed for the per protocol population in both study groups.
 
Analysis of primary endpoint: Cox regression analysis of development of the primary endpoint adjusted for age, gender, study site will be conducted in both study groups (observational and intervention) and for study intervention in the interventional group. Secondly adjusted in addition for baseline UACR, HbA1c and BP.
 
Analysis of secondary endpoints: Cox regression analysis of development of secondary endpoints in the both study groups (observational and intervention) as well within the interventional group (high- vs. low-risk), adjusted for age, gender, study site and study intervention with secondary adjustment for baseline UACR, HbA1c and BP.
 
Assessment of safety: The assessment of safety will be based primarily on the frequency of eCRF-documented AEs, laboratory abnormalities, and SAEs (see section 13.3). Occurrence and frequency of eCRF-documented AEs, SAEs and laboratory abnormalities will be summarized by treatment group.
 
In addition AEs leading to death and AEs leading to discontinuation of study medication and/or withdrawal will be summarized for the two treatment groups.
 
Final analysis plan: Statistical analysis of the data will be performed by Steno Diabetes Center. A statistical analysis plan will be written and signed before database lock and unblinding of the entire treatment code.
 
Methods for imputation and type of censoring will be clarified in the statistical analysis plan prior to database lock and unblinding.

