## 15.6 Analysis of primary endpoint

The primary endpoint is defined as time to the first occurrence of microalbuminuria (UACR >30 mg/g and <300 mg/g) in 2 out of 3 sterile first morning void urine samples with a geometric mean of UACR >30% above initial geometric mean UACR OR geometric mean > 40 mg/g in three samples. The baseline urinary albumin-to-creatinine ratios are the geometric mean of three measurements obtained during the "run-in" period.

It is expected, that the number of patients who will drop out between randomization and occurrence of microalbuminuria will be low (<15%).

If those cases where drop out occurs before sampling during the study period, prior to unblinding the treatment code it will be specified in the statistical analysis plan, whether these patients have to be considered as a treatment failure in the analysis of the primary endpoint.

The predictive value of a positive and negative test, specificity and sensitivity of the test in relation to prediction of development of the primary endpoint will be evaluated. To assess whether CKD273 classifier (the marker) improved risk prediction of the primary outcome we determined the concordance statistic (c-statistic) and Integrated Discrimination Improvement (IDI). Both parameters measure the discriminative ability of a marker in a model to distinguish between people who will or will not develop the outcome (in case of predictive methods).

The primary endpoint will be analyzed in the total population with comparisons of high- vs. low-risk pattern and active vs. placebo treatment using a Cox proportional-hazards regression model with treatment as a fixed effect; the baseline urinary albumin-to-creatinine ratio will be logarithmically transformed (base 10) as a covariate, and a two-tailed Wald chi-square test with an alpha level of less than 0.05; hazard ratios and two-sided 95 % confidence intervals will be calculated. Kaplan Meier plots of the groups will be made.

Secondly, the analyses will be adjusted for age, gender, center, HbA1c and BP. Thirdly, further adjustment for any baseline demographic variables which are significantly different between the groups and related to albuminuria at baseline will be calculated. In addition adjustment will be made for significant changes in RAAS blockade or treatment with aldosterone receptor antagonist as concomitant medication during the study period.

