2.3.3 Additional scientific objectives

To compare the rate of change in urinary albumin excretion rate in high vs. low-risk population (based on the proteomic test), and to compare the effect of spironolactone on rate of change in UACR in the intervention group.

In addition, the objective is to study the rate of change in eGFR in relation to urinary marker pattern (CKD 273) and the intervention with spironolactone.

To study the ability of urinary proteomic patterns, to predict cardiovascular or renal events during the study as well as response to intervention, in relation to study endpoints.

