5.5 Base characteristics / data description

Variable (reporting methods, [unit])

- Gender (N, % male)
- Medical history
 - o Diabetes duration (mean, SD, [years])
 - o Cardiovascular disease, hypertension, dyslipidemia [%]
 - o Retinopathy/ maculopathy (grade, [%])
 - o Smoking (grade, [%])
- Concomitant medication
 - o Use of antidiabetic medication (active substance group, [%])
 - o Use of antihypertensive agents (active substance group, [%]).
- Vital signs
 - o Systolic and diastolic blood pressure (Mean, SD, [mmHg]).
- Blood sample
 - o Creatinine, sodium, and potassium, HbA_{1c}, cholesterol, HDL, LDL, and triglycerides. (mean, SD)
- Urine sample
 - o Proteomic score (CKD273) (high, low-risk) (N, mean, [%])
 - o Urine albumin to creatinine level. (median, IQR, [mg/g])

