6.1.2 Secondary outcome

- A. Comparison of composite fatal and non-fatal cardiovascular outcome (MI, stroke, CABG, PTCA, hospitalization for heart failure and CVD) and all-cause mortality during the study.
- B. Comparison of incidence of retinopathy and frequency of laser treatment. Data collected from self-reported AEs.
- C. In addition to the categorical analysis of UACR, an analysis will be performed with changes in geometric mean of UACR throughout the study period in all patients by assessing the slope of albuminuria changes and absolute changes from inclusion to end of trial.
- D. Development of microalbuminuria (UACR >30 mg/g) in at least one morning void urine sample will be used as a secondary outcome instead of confirmed microalbuminuria.
- E. Development of macroalbuminuria (UACR >300 mg/g) in 2 out 3 first morning void urine samples).
- F. For patients with eGFR ≥ 60 ml/ min/ 1.73 m² at baseline, development of eGFR <60 ml/min/1.73m².
- G. Development of CKD stage 4 (eGFR <30 ml/min/1.73m²).
- H. Change in eGFR (slope) from baseline and from three-month post-baseline to end of study.
- I. Change in eGFR (40 % reduction) from baseline and from three-month post-baseline to end of study.
- J. Safety: Adverse Events and Serious Adverse Events. Adverse Events leading to death or discontinuation of study medication and/or withdrawal.
- K. Event of hyperkalaemia with potassium level in plasma ≥ 5.5 mmol and/or ≥ 5.8 mmol in serum at any time point.

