6.3.1.2 Analysis of secondary endpoints

Based on a 2x2 table included the primary endpoint (event/ event free) vs. risk stratification ("high"/- "low"-risk) we will calculate sensitivity, specificity and numbers need to screen for CKD273 and tested for significance using Chi-square test. In a logistic model we will added value using AUC and ROC with comparison between "high"- and "low"-risk vs. event and event-free for both primary endpoint. The logistic models will be performed both unadjusted and adjusted for age, gender, HbA_{1c}, systolic blood pressure, retinopathy, eGFR and UACR at baseline.

For the Cox-regression model a model, including adjustment for age, gender, Hba1c, systolic blood pressure, retinopathy eGFR and UACR at baseline will be comprised for secondary endpoints (see section 6.1.1 and 6.1.2, excluding 6.1.2 C, H and J).

For further clarification of the added value for discrimination, the rIDI will be calculated based on all above described Cox-regressions models with a significant HR for CKD273 in the unadjusted model for each endpoint.

To evaluate changes in UACR and eGFR over time (outcome measurement C and H in section 6.2.1) a linear mix model will be applied with adjustment for eGFR and UACR at baseline.

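### The protocol adjusts the high- versus low-risk comparison for study site, but the SAP's adjusted Cox and slope models leave site out and give no reason

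*SAP*

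**What the plan says.** **Protocol.** The synopsis says of the primary endpoint: "Cox regression analysis of development of the primary endpoint adjusted for age, gender, study site will be conducted in both study groups". Section 15.6 covers the total population, with high- versus low-risk as one of its comparisons. It starts from a Cox model with log-transformed baseline UACR and then says: "Secondly, the analyses will be adjusted for age, gender, center", followed by HbA1c and blood pressure. Section 15.7 applies the same adjustments to the secondary endpoints.

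**SAP, high- versus low-risk comparison.** The primary analysis in 6.3.1.1 is an unadjusted Cox model with a log-rank test. The adjusted version reads: "In addition, adjustment for age, gender, Hba1c, systolic blood pressure, retinopathy eGFR and UACR at baseline will be conducted". Section 6.3.1.2 repeats the list for the secondary endpoints ("including adjustment for age, gender, Hba1c, systolic blood pressure, retinopathy eGFR and UACR at baseline will be comprised for secondary endpoints"), and 6.4 repeats it for the models that exclude patients on active treatment. The UACR and eGFR slope models in 6.3.1.2 adjust only for baseline eGFR and UACR. None of these contains site.

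**Where the SAP does use site.** Section 6.3.2.2 includes it in the adjusted spironolactone versus placebo models. In the observational part it appears only in 6.3.1.3, within a list of continuous variables: "systolic blood pressure, Study site, eGFR and UACR will be tested within each stratum". The tests there are ANOVA and an interaction test in the Cox model.

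**Cardiovascular outcome.** Outcome A in SAP 6.1.2 is: "Comparison of composite fatal and non-fatal cardiovascular outcome (MI, stroke, CABG, PTCA, hospitalization for heart failure and CVD) and all-cause mortality during the study". It is not among the outcomes that 6.3.1.2 excludes from the Cox models (C, H and J), so it gets the same seven covariates. SAP 5.5 lists baseline history ("Cardiovascular disease, hypertension, dyslipidemia") and smoking, but neither prior cardiovascular disease nor smoking is a covariate in any model.

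**The concern.** Risk group is an observed characteristic, so nothing balances it across 15 sites in 10 countries. If sites with a larger high-risk share also have higher (or lower) event rates, for reasons outside the listed covariates, a model without site assigns part of that difference to CKD273. The protocol guarded against this. The SAP removes the guard without comment, yet keeps site for the randomised comparison.

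The results exposed are the adjusted hazard ratios, the rIDI values built on those models, the UACR and eGFR slopes, and the event outcomes that sites record themselves.

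A related but separate point concerns one of the SAP's stated aims: "To study the ability of urinary proteomic patterns, to predict cardiovascular or renal events during the study". If known cardiovascular history is missing from the reference model, added value for outcome A may include information that the medical history already held. SAP 6.3.1.3 itself expects known cardiovascular disease to go with the high-risk stratum and with events, but gives it only a chi-square test.

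**Working it through.** **1. Covariates side by side (high versus low risk).**

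| Source | Covariates | Site? |
|---|---|---|
| Protocol synopsis, first adjusted model | age, gender, study site | yes |
| Protocol 15.6, second step | log UACR, age, gender, center, HbA1c, BP | yes |
| Protocol 15.7, secondary endpoints | as for the primary endpoint | yes |
| SAP 6.3.1.1, 6.3.1.2 and 6.4, adjusted Cox | age, gender, HbA1c, systolic BP, retinopathy, eGFR, UACR | no |
| SAP 6.3.1.2, slopes | eGFR, UACR | no |
| SAP 6.3.2.2, randomised arms | the seven above plus study site | yes |

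The tests in SAP 6.3.1.3 do not fill the gap. An ANOVA within each stratum and an interaction test do not produce a site-adjusted CKD273 hazard ratio. Site is also a category and not a continuous measure.

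**2. Planned size of the primary contrast.** Protocol 15.1 and SAP 3.4 expect 40% (placebo), 24% (active) and 8.5% (low risk). With 1:1 allocation the high-risk average is (40 + 24)/2 = 32%. Under proportional hazards the implied ratio is ln(1 − 0.32)/ln(1 − 0.085) ≈ 4.3.

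**3. Possible size of site bias. All inputs here are assumed.** Take two equal halves of the cohort, grouped by site, with no true CKD273 effect. Let the high-risk shares be q1 and q2, and the event-rate ratio between the halves be R. Then w = q2/(q1 + q2), v = (1 − q2)/(2 − q1 − q2), and the spurious ratio is [1 + w(R − 1)]/[1 + v(R − 1)].

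- 12% vs 18%, R = 1.5 to 3: 1.05 to 1.12
- 10% vs 20%, R = 1.5 to 3: 1.08 to 1.20 (for R = 2, w = 0.667, v = 0.471, and 1.667/1.471 = 1.13)
- 5% vs 25%, R = 1.5 to 3: 1.16 to 1.42
- equal shares: 1.00

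Simulated null cohorts of 2,000 patients at 15 sites give a similar picture. The SDs are between-site, in high-risk log-odds and in log-hazard, with the stated correlation. Results are from two runs, of 300 and 1,000 cohorts per scenario, with about 264 and 290 to 305 events.

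| SD, correlation | Unadjusted HR | Rejection at 5%, unadjusted vs site-stratified |
|---|---|---|
| 0.5, 0.5 | 1.12; 1.10 | 15% vs 5%; 13% vs 4% |
| 0.3, 0.5 | 1.04; 1.03 | 9% vs 6%; 7% vs 5% |
| 0.5, −0.5 | 0.91; 0.89 | 12% vs 4% (second run) |

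These figures compare an unadjusted model with a site-stratified one. They do not measure what remains after the seven SAP covariates.

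**4. Can the data carry site?** Planned events are 150 × 0.40 + 150 × 0.24 + 1,700 × 0.085 = 240.5. CKD273 plus seven covariates is 8 parameters, or 30 events per parameter. Adding 14 site indicators makes 22 parameters, or 10.9. For the SAP's 1,811 patients at an assumed 15% high risk, events are 271.65 × 0.32 + 1,539.35 × 0.085 ≈ 218, giving 27 and 9.9. Stratifying the Cox model by site adds no parameters.

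**5. Prior cardiovascular disease and outcome A (assumed inputs).** For prevalence pH and pL and event ratio R, the bias factor is [1 + pH(R − 1)]/[1 + pL(R − 1)]. With 30% vs 15% and R = 2 to 3 it is 1.13 to 1.23. With 20% vs 15% it is 1.04 to 1.08. With equal prevalence it is 1.00. The formula treats prior disease as independent of the seven covariates, so it overstates the bias where they are related. The documents give no expected cardiovascular event count, so the check in step 4 cannot be repeated for outcome A.

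**The case against.** Much of the opposing case stands.

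- **Measurement is partly protected.** UACR is analysed centrally (Protocol 10.9) and CKD273 in one laboratory (10.10), under common freezing and dry-ice rules. Local creatinine must use a traceable standardised method (10.8). For the primary endpoint, site would therefore act mainly through case mix, care and sample handling, and the listed covariates absorb some of the case mix. Site matters more for eGFR outcomes and site-recorded events.
- **The bias figures rest on assumptions.** The documents supply neither the between-site SDs nor the correlation. The SD 0.3 contrast is weak: in the 300-cohort run it is about 27 versus 17 rejections.
- **Site in the randomised comparison is correct.** Center is a randomisation stratum (SAP 3.2). A reader might infer that the SAP put site in the wrong place, but the issue is only its absence elsewhere.
- **The unadjusted primary analysis asks a legitimate question:** does the test predict at all? Protocol 15.6 brings in center only at the second step. A reader might infer that the unadjusted analysis should also be stratified; that is not needed.
- **Prior cardiovascular disease and smoking were never named as covariates in the protocol.** Its data-driven third step concerns demographic variables related to albuminuria and may not reach them. A reader might infer that the SAP dropped them, but it did not. Entry is also stricter than a three-month window alone: exclusion 13 covers NYHA III–IV heart failure and unstable angina as well as MI, stroke, PTCA or CABG within three months. Older MI, stroke and revascularisation remain eligible.

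None of this explains why site left the adjusted models.

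**Conclusion.** The point holds as an unexplained departure from the protocol: site is missing from the adjusted high- versus low-risk Cox models and from the slope models. It should be corrected or justified.

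The size of any bias cannot be read from the documents. Under the assumed SDs of 0.3 to 0.5 and correlation 0.5, an unadjusted null hazard ratio would be about 1.03 to 1.12. Less would be expected after the seven covariates, and a negative correlation would push the ratio below 1.

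A reader might infer that the primary test loses its 5% level or that the main result could be an artefact of site. The documents do not support that. The raised rejection rates need both a true null and an assumed site correlation, and a bias of this size is far below the planned ratio of about 4.3. It could matter for modest adjusted, added-value, slope or cardiovascular results.

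The cardiovascular covariates are a secondary improvement and not a departure from the protocol.

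**What to change.** Before unblinding, amend the SAP as follows.

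1. Keep the unadjusted Cox and log-rank analysis in 6.3.1.1 as it is.
2. Stratify the adjusted high- versus low-risk Cox models in 6.3.1.1, 6.3.1.2 and 6.4 by study site, or state why the protocol's adjustment was dropped.
3. Include site in the UACR and eGFR slope models in 6.3.1.2.
4. In 6.3.1.3, move study site to the categorical variables.
5. As a secondary improvement, for outcome A add prior cardiovascular disease and smoking to the adjusted model and to the rIDI reference model, if the number of cardiovascular events allows. Added value is then judged beyond known history.

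The cost is SAP wording. Site is part of the patient identifier, and the two cardiovascular variables are already baseline items. The downside is that very small sites contribute less information to a stratified estimate.
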